cDMARD	conventional disease-modifying anti-rheumatic drug
CI	confidence interval
CL	systemic clearance
Cmax	maximum observed concentration
CRP	C-reactive protein
CTCAE	common terminology criteria for adverse event
DAS28-CRP	Disease Activity Score in 28 Joints Using C-reactive Protein
ECG	electrocardiogram
FACIT-Fatigue	Functional Assessment of Chronic Illness Therapy - Fatigue
HAQ	Health Assessment Questionnaire
IL-6	interleukin-6
IP	Investigational product
MDGA	physician global assessment of disease activity
MedDRA	Medical Dictionary for Regulatory Activities
MMRM	mixed-effect model for repeated measures
MTX	methotrexate
LSMeans	least square means
PD	Pharmacodynamic(s)
PGA	patient global assessment of disease activity
PK	Pharmacokinetic(s)
PT	preferred term
QTc	corrected QT interval
RA	rheumatoid arthritis
RF	rheumatoid factor
sCD40L	soluble CD40 ligand
SDAI	Simplified Disease Activity Index
SE	standard error
SJC28	28 swollen joint count
SOC	system organ class

Abbreviation or Specialized Term	Definition
SPP	statistical programming plan
$t_{1/2}$	terminal elimination half-life
TEAE	treatment-emergent adverse event
TEAESI	treatment-emergent adverse event of special interest
TESAE	treatment-emergent serious adverse event
TJC28	28 tender joint count
VAS	visual analog scale
WHO	world health organization

1 INTRODUCTION

This document describes the statistical analysis for protocol VIB4920.P2.S3, a Phase 2 randomized, double-blind, placebo controlled, parallel-cohort study to evaluate the safety, efficacy, and pharmacokinetics (PK) of VIB4920 in adults with moderate-to-severe rheumatoid arthritis (RA).

2 STUDY OVERVIEW

2.1 Study Objectives and Endpoints

The objectives and corresponding endpoints are listed in [Table 1](#) below:

Table 1 Study Objectives and Endpoints

[figure not shown]
[figure not shown]
Primary objective	Endpoints/variables

 • To evaluate the effect of VIB4920 on disease activity as assessed by a composite measure in subjects with adult-onset RA 	
 • Change in Disease Activity Score in 28 Joints Using C-reactive Protein (DAS28-CRP) from baseline to Day 113

 • To evaluate the safety and tolerability of VIB4920 in subjects with adult-onset RA 	
 • Incidence of treatment emergent adverse events (TEAEs), treatment emergent serious adverse events (TESAEs), and treatment emergent adverse events of special interest (TEAESIs)
Secondary objectives	Endpoints/variables

 • To characterize the PK of VIB4920 in subjects with adult-onset RA 	
 • PK profile

 • To evaluate the pharmacodynamic (PD) effect of VIB4920 in subjects with adult-onset RA 	
 • Total soluble CD40 ligand (sCD40L)

 • To evaluate the immunogenicity of VIB4920 in subjects with adult-onset RA 	
 • Anti-drug antibodies (ADA)

 • To evaluate the effect of VIB4920 on autoantibodies in subjects with adult-onset RA 	
 • Rheumatoid factor (RF) • Anti-cyclic citrullinated peptide antibody (ACPA)

 • To assess the effect of VIB4920 on clinical remission as assessed by a composite measure in subjects with adult-onset RA 	
 • DAS28-CRP < 2.6

 • To evaluate the duration of clinical response to VIB4920 as assessed by time to institution of rescue therapy 	
 • Time to start of new treatment for RA (rescue medication)
	
	
	

Table 1 Study Objectives and Endpoints

•	■	■	■
	■	■	■
■	■	■	■
■	■	■	■

[figure not shown]
2.2 Study Design

This is a multicenter, randomized, double-blind, placebo-controlled, parallel-cohort study to evaluate the safety, efficacy, and PK of VIB4920 administered intravenously in adults with active, moderate-to-severe adult-onset RA who have had an inadequate response to methotrexate, conventional disease-modifying anti-rheumatic drug (cDMARD), or an anti-TNF α agent.

After a screening period of up to 28 days, approximately 75 subjects will be randomized in a 1:1:1:1:1 ratio into 5 cohorts (treatment groups) as shown in [Figure 1](#) below. Subjects are to be followed on their stable background anti-RA therapy at least through 12 weeks (Day 85), at which time rescue therapy may be instituted. All subjects are followed at least through the primary analysis (Day 113), and those who have not instituted rescue therapy will be followed through Day 309 to determine the duration of clinical response.

A study schematic is presented in Figure 1.

Figure 1 Study Flow Diagram

2.3 Sample Size

The planned sample size of 75 subjects (15 subjects per treatment group) will provide approximately 80% power to detect a difference of 1.2 in mean change from baseline to Day 113 in DAS28-CRP (assumed standard deviation of 1.25) between the VIB4920 and placebo treatment groups at a 2-sided alpha level of 0.10 using a 2-sample t-test.

3 STATISTICAL METHODS

3.1 General Considerations

All statistical calculations will be primarily performed using SAS® System Version 9.4 or higher. Categorical data will be summarized by the frequency counts and percentage of subjects in each category. Continuous variables will be summarized by descriptive statistics, including number of observations, mean, standard deviation, median, first quartile, third quartile, minimum, and maximum.

3.1.1 Definition of Baseline

Unless otherwise specified, baseline will be defined as the last non-missing valid observation prior to the first administration of IP. In cases where baseline measurements are taken on the same day as IP and no times are reported, it will be assumed that these measurements are taken prior to IP being administered.

3.1.2 Analysis Windows

Analysis visit windows will be used for all visit-based assessments to map longitudinal observations to scheduled visits and thereby allow for by-visit analyses, since not all assessments are performed on the scheduled day. Unless otherwise specified, all longitudinal efficacy, safety, and biomarker data analyses will be based on the analysis visit windows. The analysis visit windows will be calculated by bisecting the interval between adjacent scheduled visit days except for the first post-treatment visit. The first post-treatment visit will start at Day 2. The detailed analysis visit windows will be specified in the statistical programming plan (SPP).

The actual assessment day will be mapped to the windows defined for each scheduled study visit with following rules:

- If more than one assessment falls within a visit window, the closest non-missing assessment to the scheduled day will be used in the analysis.
- If 2 non-missing assessment actual dates are equidistant from the target day, the later visit will be used in the analysis.
- For retest values of laboratory data, the retest value (the last valid observation assessed on the same visit day) will be chosen.

3.2 Protocol Deviations

All protocol deviations will be classified as either major protocol deviations or minor protocol deviations. The major protocol deviations are considered as the important protocol

deviations, which may significantly impact the completeness, accuracy, and/or reliability of the study data or that may significantly affect a subject's rights, safety, or well-being. All the protocol deviations will be listed, and the major protocol deviation will be summarized. Some classifications of major protocol deviations are listed below.

- Did not meet inclusion criteria or met exclusion criteria.
- Blindness of treatment assignment was broken by site investigator
- Received prohibited concomitant medication
- Serious breach of good clinical practice.

The list may be updated and will be finalized and documented prior to the database lock for the primary analysis.

3.3 Analysis Sets

3.3.1 Full analysis set

The full analysis set includes all randomized subjects who received any dose of IP. Subjects will be analyzed according to the treatment randomized. The efficacy analysis will be based on the full analysis set.

3.3.2 Safety analysis set

The safety analysis set includes all subjects who received any dose of IP. Subjects will be analyzed according to the treatment that they actually received. The safety and ADA analyses will be based on the safety analysis set.

3.3.3 Pharmacokinetics analysis set

The PK analysis set includes all subjects who received IP and have at least one quantifiable plasma PK observation post-first dose. Subjects will be analyzed according to the treatment that they actually received. PK analyses will be based on the PK analysis set.

3.4 Study Subjects

3.4.1 Subject Disposition

A summary of subject disposition will be presented using the categories presented below.

- Screened
- Screen failed with reasons
- Randomized
- Randomized but not treated
- Randomized and treated

- Completed treatment
- Discontinued treatment with reasons
- Completed study
- Discontinued study with reasons

A Kaplan-Meier curve of the time to study discontinuation will be provided.

3.4.2 Demographics, Baseline Characteristics, and Medical History

The demographics (age, gender, race, ethnicity, height, weight, and body mass index) will be summarized by treatment group and overall for the full analysis set.

A summary of baseline disease characteristics, by treatment group and overall for the full analysis set will include DAS28-CRP, [REDACTED], MDGA, PGA, CDAI, SDAI, HAQ, CRP, ACPA (positive/negative), RF (positive/negative), and presence of rheumatoid nodules.

Significant medical history findings will be summarized by Medical Dictionary for Regulatory Activities (MedDRA) system organ class (SOC) and preferred term (PT) by treatment group and overall for the full analysis set.

3.4.3 Investigational product Exposure

The number of doses received, amount (mg) of the IP received, durations of the IP exposure, and total subject years exposure will be summarized by treatment using the safety analysis set.

- Duration of the IP exposure is defined as (last dose date + 28 – first dose date + 1)
- The amount of IP received: if a subject received partial dose at a dosing visit, then the amount of IP at that dosing visit will be estimated based on the actual volume administered.
- Treatment compliance for an individual patient = (Total number of doses received)/(Total number of doses planned per protocol) $\times 100\%$.

Number of subjects with at least one entire dose not administered, infusion interrupted, and infusion rate decreased will be summarized using the safety analysis set.

3.4.4 Prior and Concomitant Medications

Number (%) of subjects who receive prior medications and concomitant medications will be summarized by world health organization (WHO) Drug dictionary Anatomical Therapeutic Chemical (ATC) category and PT based on the safety analysis set. At each level of summarization, a subject is counted once if he/she reported one or more medications at that level. The prior and concomitant medications are defined as below.

- Prior medications are defined as medications with a stop date occurring before the first IP administration date.
- Concomitant medications are defined as medications with a stop date on or after the first IP administration date.

RA medication history will be summarized by medication category (cDMARD, biologic DMARD [bDMARD], JAK Inhibitor, etc.). The reasons for treatment discontinuation will also be summarized.

Use of RA-related medications at baseline, defined as all RA-related medications with an intake at the date of first dose of IP (ie, start date on or before the date of first dose and end date on or after date of first dose or ongoing) will be summarized for the full analysis set. The number and percentage of subjects who receive rescue therapy will also be summarized for the full analysis set.

Rescue therapy is any new or intensified immunosuppressive, cDMARD, or bDMARD treatment for RA, including:

- Initiation of or increase in dose of any cDMARD
- Initiation of bDMARD therapy or Janus kinase inhibitor therapy
- Increase in baseline corticosteroid dose
- Intraarticular steroid injection > 40 mg methylprednisolone (or its equivalent) OR more than one intraarticular steroid injection of any dose. One intraarticular steroid injection ≤ 40 mg methylprednisolone in one joint is permitted and not considered rescue therapy

The missing start/stop date of medications will be imputed as appropriate and the details of the imputation will be included in the SPP.

3.5 Efficacy Analyses

3.5.1 Primary Efficacy Endpoint(s) and Analyses

3.5.1.1 Primary efficacy endpoint

The primary efficacy endpoint is change from baseline DAS28-CRP to Day 113.

DAS28-CRP:

DAS28-CRP values will be calculated as follows ([Wells et al, 2009](#)):

$$\text{DAS28-CRP} = 0.56 \times \sqrt{(\text{TJC28})} + 0.28 \times \sqrt{(\text{SJC28})} + 0.014 \times \text{PGA} (0 - 100 \text{ mm visual analogue scale [VAS]}) + 0.36 \times \ln(\text{CRP}[\text{mg/L}] + 1) + 0.96$$

Low disease activity is defined as DAS28-CRP ≤ 3.2 , and an improvement of DAS28-CRP score > 0.6 defines a responder. Remission is defined as DAS28-CRP < 2.6 .

3.5.1.2 Primary efficacy analysis

The primary efficacy endpoint will be analyzed using the mixed-effect model for repeated measures (MMRM) approach for the full analysis set. The model will include fixed effects for treatment, visit, visit by treatment interaction, and baseline DAS28-CRP score.

From the model, the estimated treatment effect (ie the difference [VIB4920 – placebo] in least square means [LSMeans]) at Day 113 will be obtained, together with a two-sided 90% confidence interval (CI), standard error (SE) and p-value. The significance of treatment effect will be tested by using a two-sided test at significance level α of 0.1. Additionally, estimates of the LSMeans for each treatment group will be obtained, together with the associated SE.

Longitudinal presentations of results over time based on the same analysis will be created.

Model assumptions for MMRM will be checked with graphical displays (residual plots and a quartile-quartile plot). If the model assumptions are not met, appropriate data transformations or the non-parametric approaches will be used.

3.5.1.3 Handling plan for Intercurrent Events

Rescue medication use:

For subjects who take rescue medications defined in section 3.4.4, the data collected after administration of the rescue medications will not be included in the primary analysis. This approach attempts to reduce the confounding effects of rescue medications.

Treatment discontinuation:

Subjects who discontinue IP without receiving rescue medications will be asked to come to scheduled evaluations until the end of study. The data collected after discontinuation of IP will be included in the analysis.

3.5.1.4 Handling plan for missing data

Missing data will be handled using the MMRM approach. If any of the DAS28-CRP component cannot be evaluated at a visit, that component will be imputed using last observation carried forward (LOCF) approach.

3.5.1.5 Sensitivity analysis of primary efficacy endpoint

The sensitivity analysis will be performed for the primary efficacy endpoint using the same model as the primary analysis with the following handling plan for the rescue medication use and treatment discontinuation.

- Impute result after rescue medications using the worst score including baseline. For subjects who discontinue IP without receiving rescue medications, include data collected after discontinuation of study treatment.
- Include data collected after rescue medications and data collected after discontinuation of study treatment.

CRP, RF, and ACPA values were provided unblinded by the central laboratory in violation of the protocol starting from 20Jan2021. Reports were required to be accessed by site, signed by investigator, and filed, and thus the assumption is that a very wide set of people at site, CRO and sponsor had access to these potentially unblinding data. The blinding was restored on 27Jan2021. After consulting with DSMB statistician, we will perform a sensitivity analysis by removing data that might have introduced bias (see Appendix 1).

3.5.1.6 Subgroup analyses of primary endpoint

No subgroup analyses are planned for the primary endpoint due to the small sample size per treatment group in the study.

3.5.1.7 Multiplicity adjustment

The type I error rate will be controlled at 0.1 level (2-sided) for the primary efficacy analysis using the following sequential testing strategy.

1. The primary endpoint will be tested for Cohort 1 (VIB4920 1500 mg on Days 1, 15, 29, and 57) compared with placebo
2. If p-value is ≤ 0.1 in step 1, the primary endpoint will be tested for Cohort 3 (VIB4920 3000 mg on Days 1 and 57) compared with placebo
3. If p-value is ≤ 0.1 in both step 1 and step 2, the primary endpoint will be tested for Cohort 2 (VIB4920 1500 mg on Days 1 and 57) and Cohort 4 (VIB4920 3000 mg on Day 1) compared with placebo using the Hochberg method ([Hochberg, 1988](#)).

3.5.2 Secondary Efficacy Endpoints and Analyses

3.5.2.1 Secondary efficacy endpoints

The secondary efficacy endpoints are as follows:

- The proportion of subjects with clinical remission defined as DAS28-CRP < 2.6 at Day 113
- Time to start of rescue medication
- Change in RF and ACPAs from baseline to Day 113

3.6 Safety Analysis

3.6.1 Adverse Events

In general, if an AE onset is on or after the first dose of IP administration, the AE will be considered as a TEAE. Otherwise, the AE will be considered as a non-treatment emergent AE.

An overall summary table will be showing the number and percentage of subjects with at least 1 event in any of the following categories: TEAE, TESAE, TEAE with outcome of death, TEAE leading to discontinuation of IP, grade 3 or higher TEAE, serious and/or grade 3 or higher TEAE, IP related TEAE, IP related TESAE.

AEs will be coded using the most recent version of MedDRA. All TEAEs will be summarized overall and by MedDRA SOC and PT, by severity and by relationship to IP. Specific AEs will be counted once for each subject for calculating rates, but all events will be presented in subject listings. In addition, if the same AE occurs multiple times within a particular subject, the highest severity and level of causality will be reported.

The TEAEs, TESAEs, TEAEs resulting in death, TEAEs leading to discontinuation of IP, Grade 3 or higher TEAEs, IP related TEAEs, and IP related TESAEs will be summarized by SOC and PT. TESAEs will be summarized by SAE criteria as well. In addition, a summary of TEAEs sorted by frequency will be presented by PT.

An AESI is one of scientific and medical interest specific to understanding of the IP. AESIs for this protocol include:

- Thrombotic and embolic events
- Anaphylaxis and clinically significant (Grade 3 or higher) hypersensitivity reactions
- Severe Infusion-related reactions (common terminology criteria for adverse event (CTCAE) Grade 3 or higher)
- Immune complex disease
- Severe (Grade 3 or higher) and/or opportunistic infections
- Hepatic function abnormality (meeting the definition of Hy's Law)
- Malignant neoplasm

TEAESIs will be summarized by SOC and PT.

Listings will be provided for all TEAEs and non-treatment emergent AEs.

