3.1.2 Primary Endpoints

- Change in DAS28-CRP from baseline to Day 113.
- The incidence of TEAEs and treatment-emergent serious adverse events (TESAEs) and treatment-emergent AEs of special interest (AESIs) during the study. AESIs include:
 - Thrombotic and embolic events
 - Anaphylaxis and clinically significant (Grade 3 or higher) hypersensitivity reactions (see [Appendix 1](#))

- Severe infusion-related reactions (Common Terminology Criteria for Adverse Events [CTCAE] Grade 3 or higher)
- Immune complex disease
- Severe (Grade 3 or higher) and/or opportunistic infections
- Hepatic function abnormality meeting the definition of Hy's Law (see [Appendix 2](#))
- Malignant neoplasm

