7.4.2 Rescue Therapy

Rescue therapy is any new or intensified immunosuppressive, conventional, or bDMARD treatment for RA, including:

- Initiation of or increase in dose of any cDMARD
- Initiation of a bDMARD therapy or JAK inhibitor therapy
- Increase in baseline corticosteroid dose
- Intraarticular steroid injection > 40 mg methylprednisolone (or its equivalent) OR more than one intraarticular steroid injection of any dose. One intraarticular steroid injection ≤ 40 mg methylprednisolone in one joint is permitted and not considered rescue therapy.

If a subject receives rescue therapy prior to the final dose of IP, IP will be discontinued (Section [6.5.1](#)).

Subjects administered rescue therapy do not need to be followed until Day 309 but can complete the study at or after Day 113. Subjects must also complete a 3-month safety follow-up period after the final dose of IP and must return for at least one visit after initiating rescue therapy to complete remaining assessments ([Table 8](#)).

Table 8 Alternate Study Completion Schedules Following Rescue Therapy

Last Dose Prior to Rescue Therapy	Last Study Visit
≤ Dose 3 (Day 29 ± 3d)	Day 113 OR + 1 visit post-initiation of rescue therapy, whichever is later
≥ Dose 4 (Day 57 ± 3d)	Day 141 OR + 1 visit post-initiation of rescue therapy, whichever is later

Note: All actions include the required Day 113 visit, 3 months of follow-up, and one visit post-initiation of rescue therapy.

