8.1 Definitions

- **Adverse event** – An AE is any untoward medical occurrence associated with the use of an intervention in humans whether or not it is considered intervention-related.
- **Serious adverse event** – A SAE is considered “serious” if, in the view of either the Investigator or Sponsor, it results in any of the following outcomes:
 - Death
 - A life-threatening AE. (An event is considered “life-threatening” if, in the view of either the Investigator or Sponsor, its occurrence places the patient or subject at immediate risk of death. It does not include an AE or suspected adverse reaction (SAR) that, had it occurred in a more severe form, might have caused death.)
 - Inpatient hospitalization or prolongation of existing hospitalization
 - A persistent or significant incapacity or substantial disruption of the ability to conduct normal life functions
 - A congenital anomaly/birth defect
 - Important medical events that may not result in death, be life-threatening, or require hospitalization may be considered serious when, based upon appropriate medical judgment, they may jeopardize the patient or subject and may require medical or surgical intervention to prevent one of the outcomes listed in this definition. Examples of such medical events include allergic bronchospasm requiring intensive treatment in an emergency room or at home, blood dyscrasias or convulsions that do not result in inpatient hospitalization, or the development of drug dependency or drug abuse.
- **Causality or relatedness:** The Investigator is required to provide an assessment of the relationship of AEs and SAEs to the IP. An event will be considered “not related” to use of IP if any of the following tests are met:

- An unreasonable temporal relationship between administration of the IP and the onset of the event (eg, the event occurred either before, or too long after, administration of the IP for it to be considered IP-related)
- A causal relationship between the IP and the event is biologically implausible (eg, death as a passenger in an automobile accident)
- A clearly more likely alternative explanation for the event is present (eg, typical adverse reaction to a concomitant drug and/or typical disease-related event)

Individual AE/SAE reports will be considered “related” to use of the IP if the “not related” criteria are not met.

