8.3 Reporting Adverse Events

All AEs (related and unrelated) will be recorded from written ICF signature up to the end of the study, whether or not they are related to the study. Any SAEs considered related to the IP and discovered by the Investigator at any time after the study should be reported.

All SAEs must be reported within 24 hours by submitting a SAE Report Form by email to:

[REDACTED]
[REDACTED]

Alternatively, the SAE Report Form can be submitted by fax to:

[REDACTED]
[REDACTED]

Additional follow-up information, if required or available, should all be reported within one business day of receipt, should be completed on a follow-up SAE form, placed with the original SAE information and kept with the appropriate section of the eCRF and/or study file.

The designated Sponsor representative (ICON) will work with the Investigator to ensure that all the necessary information is provided within one calendar day of initial receipt for fatal and life-threatening events and within 5 calendar days of initial receipt for all other SAEs.

Viela Bio or designee is responsible for notifying the relevant regulatory authorities of certain events. It is the PI's responsibility to notify the IRB or IEC of all SAEs that occur at his or her site. Investigators will also be notified of all unexpected, serious, drug-related events (7/15 Day Safety Reports) that occur during the clinical trial. Each site is responsible for notifying its IRB or IEC of these additional SAEs.

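### RA flares that sites report as AEs count in the TEAE and TESAE incidence, and no planned table gives the number of subjects with a non-RA TEAE

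*SAP*

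**What the plan says.** Protocol 3.1.2 makes this a primary endpoint: "The incidence of TEAEs and treatment-emergent serious adverse events (TESAEs) and treatment-emergent AEs of special interest (AESIs) during the study".

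Three rules decide what enters the first two components:

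- Protocol 8.1, AE definition: "An AE is any untoward medical occurrence associated with the use of an intervention in humans whether or not it is considered intervention-related". It has no exception for the disease under study.
- Protocol 8.3, recording: "All AEs (related and unrelated) will be recorded from written ICF signature up to the end of the study".
- SAP 3.6.1, treatment emergence: "if an AE onset is on or after the first dose of IP administration, the AE will be considered as a TEAE".

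Protocol 8.1 also gives, as an example of a more likely alternative explanation that makes an event not related to IP, a "typical adverse reaction to a concomitant drug and/or typical disease-related event". Disease events are therefore foreseen among recorded AEs, and the text deals with their causality, not with their exclusion.

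For display, SAP 3.6.1 says: "An overall summary table will be showing the number and percentage of subjects with at least 1 event in any of the following categories". The eight categories are any TEAE, TESAE, fatal TEAE, TEAE that led to stopping IP, Grade 3 or higher, serious and/or Grade 3 or higher, and the IP-related TEAE and TESAE. The same section plans SOC and PT tables for most of these, a PT table by frequency, separate AESI tables and listings. Protocol 9.5.3 makes all safety analysis descriptive.

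**The concern.** Worsening RA is an efficacy outcome in this trial. The first study hypothesis (Protocol 2.3) is that VIB4920 lowers disease activity, and time to rescue is a secondary efficacy endpoint. If the hypothesis is right, flares are rarer on VIB4920. A row that counts each subject once for any TEAE then adds an outcome that favours the drug to harms that may not, and the two can cancel.

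Readers do use this comparison. Protocol 2.1.5.1 supports the tolerability claim from the earlier RA study by the balance of TEAEs between placebo and the active groups. At stake is whether the same statement, made from this trial's overall table, describes harms or a mixture of harms and lack of efficacy.

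**Working it through.** **Inputs.** The documents give no TEAE or flare rates and no safety test, margin or power, so there is no safety figure to reproduce. The only design calculation is the efficacy sample size, and this point does not depend on it. From the documents: 15 subjects per group and the counting rules above. All rates below are assumptions.

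**Formula.** Let h be the proportion of subjects with any non-RA TEAE and f the proportion with a reported RA-worsening TEAE, taken as independent. Subscript 0 is placebo and 1 is VIB4920.

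- P(any TEAE) = 1 - (1 - h)(1 - f)
- Apparent difference = (1 - h0)(1 - f0) - (1 - h1)(1 - f1)
- Shortfall from the true difference h1 - h0 = (1 - h0)f0 - (1 - h1)f1

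The shortfall is positive whenever f1 < f0 and h1 ≥ h0. Under independence, the direction of this mechanism therefore does not depend on the rates chosen. Its size does.

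**Numbers put in, h = 50% v 60% (true +10 points).**

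- Flares 10% v 5%: placebo 1 - 0.50 × 0.90 = 55.0%; VIB4920 1 - 0.40 × 0.95 = 62.0%; difference +7.0.
- Flares 25% v 5%: placebo 1 - 0.50 × 0.75 = 62.5%; VIB4920 62.0%; difference -0.5.

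**Range for a true +10 points (apparent difference, in points).**

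| Non-RA TEAEs, placebo v VIB4920 | Flares 10% v 5% | Flares 25% v 5% | Flares 35% v 10% |
|---|---|---|---|
| 40% v 50% | +6.5 | -2.5 | -6.0 |
| 50% v 60% | +7.0 | -0.5 | -3.5 |
| 60% v 70% | +7.5 | +1.5 | -1.0 |

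**Larger excess, h = 40% v 60% (true +20 points).** Flares of 10% v 5% leave +16, 20% v 5% leave +10, 30% v 10% leave +6, and 40% v 10% leave 0.

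**Can the PT tables recover the missing count?** Subjects can have both kinds of event. If A is the proportion with any TEAE and R the proportion with RA worsening, the proportion with any non-RA TEAE lies between A - R and A. In the 25% v 5% example:

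- Placebo: 62.5 - 25 = 37.5% to 62.5% (assumed value 50%).
- VIB4920: 62.0 - 5 = 57.0% to 62.0% (assumed value 60%).
- Difference: from 57.0 - 62.5 = -5.5 to 62.0 - 37.5 = +24.5 points.

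From these two counts alone, the tables do not determine even the sign.

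**Precision.** One subject of 15 is 6.7 points. The standard error of 60% minus 50% at 15 per group is √(0.6 × 0.4/15 + 0.5 × 0.5/15) = 18 points.

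**The case against.** The strongest case against runs as follows.

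- **The premise is inferred.** No text says that a flare is to be entered as an AE. The eCRF Completion Guidelines named in Protocol 11.5.1 may settle it and are not available. A reader might infer that worsening RA *is* recorded as a TEAE. The documents support only that nothing exempts it, so a reported flare counts. This stands, and the point is conditional on reporting.
- **The endpoint is wider than these rows.** A reader might infer that the whole primary safety endpoint is distorted. It is not. RA worsening is not an AESI, and AESIs are tabulated separately. The Grade 3 or higher and discontinuation rows are not in the endpoint at all. This stands.
- **Discontinuation.** Protocol 7.4.2 says "If a subject receives rescue therapy prior to the final dose of IP, IP will be discontinued", and a reader might infer that lack of efficacy will appear as a tolerability stop. However, rescue is the trigger there, not an AE. Protocol 6.5.2 records an AE and lack of efficacy as different reasons, and SAP 3.4.1 tabulates treatment discontinuation by reason. The row is affected only if a flare AE is also recorded as leading to the stop. The argument is secondary.
- **Other tables show the harms.** An excess of infections, for example, stays visible in its own SOC and PT lines, and the IP-related rows should drop most disease events. This largely stands. Still, the related rows rest on investigator attribution and drop other unrelated events. The non-RA count could be built from listings, but terms chosen after unblinding would not be prespecified.
- **The net direction is not established.** Under Protocol 7.4.2 (Table 8), rescued subjects can finish at Day 113 or 141 instead of Day 309, or at a later visit after rescue. If rescue is commoner on placebo, AE observation is shorter there, which pushes the crude comparison against VIB4920. This stands, and the extra rows do not correct it.
- **Noise.** With a standard error of about 18 points and no safety test, no formal conclusion can be biased. This stands. The harm is to how headline percentages are read.

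**Conclusion.** The point holds as a reporting weakness of modest importance. Flares that sites report as AEs enter the TEAE and TESAE incidence, and no planned table gives the number of subjects with any other TEAE. If flares are rarer on VIB4920, the crude rows can understate a non-RA excess. The loss ranges from small (+7 of +10 points with flares of 10% v 5%) to complete (-0.5 with 25% v 5%).

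This rests on assumed rates, on independence of flares and other TEAEs, and on sites reporting flares as AEs. The documents do not show that masking will occur, nor its net direction once shorter follow-up after rescue is counted. Redacted text and the statistical programming plan could not be seen and are not counted as gaps.

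**What to change.** In SAP 3.6.1, keep all planned rows and add four to the overall summary table:

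1. TEAE excluding RA-worsening events
2. TESAE excluding RA-worsening events
3. Grade 3 or higher TEAE excluding RA-worsening events
4. RA-worsening TEAEs by themselves

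Define RA worsening by a list of MedDRA PTs, fixed blind before database lock for the primary analysis. Protocol 9.5.3 already sets that deadline for the AESI search criteria.

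The cost is SAP wording, one short list and four table rows, with no new data. The non-RA rows may look less favourable to VIB4920. The list cannot repair uneven reporting of flares between sites, but the fourth row will show how many were reported in each group.
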